7.6 Causality Assessment of Adverse Events

For all AEs, the Principal Investigator will provide an assessment of causal relationship to the study medication. The causality assessment must be recorded in the subject's source documents and on the AE CRF. Causal relationship will be classified according to the following criteria:

1. *Unrelated*: The event is clearly due to causes other than the active study drug.

2. *Unlikely*: The event is doubtfully related to active study drug. The event was most likely related to other factors such as the patient's clinical state, concomitant drugs or other therapeutic interventions.
3. *Possible*: The event follows a reasonable temporal sequence from the time of active study drug administration but could have been produced by other factors such as the patient's clinical state, therapeutic interventions or concomitant drugs.
4. *Probable*: The event follows a reasonable temporal sequence from the time of active study drug administration and follows a known response pattern to the drug. The toxicity cannot be reasonably explained by other factors such as the patient's clinical state, therapeutic interventions or concomitant drugs.
5. *Definite*: The event follows a reasonable temporal sequence from the time of active study drug administration, follows a known response pattern to the drug, cannot be reasonably explained by other factors such as the patient's condition, concomitant drugs or therapeutic interventions, AND either occurs immediately following active study drug administration, improves on stopping the study drug, or reappears on re-exposure.

7.6.1 Potential Adverse Events Associated with ORMD-0801

Hypoglycemia and associated symptoms (e.g., weakness, dizziness, shakiness, increased sweating, palpitations, or confusion), have been associated with insulin administration, including ORMD-0801. Animal reproductive studies have not been conducted with ORMD-0801. It is not known whether ORMD-0801 can cause fetal harm when administered to a pregnant woman. It is also not known whether this product is excreted in human milk. Pregnant or breastfeeding women are excluded from this study.

Long-term animal studies have not been completed to assess whether ORMD-0801 impairs fertility.

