3.2.1 Screen Failure

A screen failure is defined as a subject who has signed the ICF, does not meet all the entry criteria outlined in Section 4 of this protocol. Note that this includes assessments through Visit 1 (up to Days -42), prior to receiving IMP.

The Investigator is responsible for keeping a record of all subjects screened for entry into the study and subsequently excluded. The reason(s) for exclusion will be recorded in the source documents and on the Screening log.

Subjects previously screen failed on eligibility criteria, may be re-screened after re-consenting at the discretion of the treating physician.

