4 STUDY SUBJECT SELECTION

4.1 Inclusion Criteria

Each subject must meet all of the following criteria to be eligible for the study:

Inclusion Criteria

1. Male or female aged 18-70 years.
2. BMI ≥ 25
3. Known type 2 DM according to American Diabetic Association (one of the three needed): Fasting Plasma Glucose ≥ 126 mg/dl or 2h postprandial (PG) following 75g OGTT ≥ 200 mg/dl or HbA1C $> 6.5-11\%$ ²⁸ or on treatment with at least one and no more than-three of the following oral anti-diabetic medications metformin, sulfonylurea, DPP-4 inhibitors, oral GLP-1 receptor agonists (semaglutide), SGLT-2 inhibitor or Thiazolidinediones (TZDs).
4. Diagnosis of NAFLD by non-invasive determination of hepatic steatosis grade S1, defined as hepatic steatosis $> 8\%$, by MRI- PDFF and CAP FibroScan ≥ 238 dB/m.
5. Liver enzyme abnormalities: ULN ≤ 5 times.
6. Fibrosis score $1 \leq F \leq 3$ as defined by FibroScan measurement (Liver stiffness measurement, LSM) of $6 \leq LSM \leq 12$ kPa.
7. Signature of the written informed consent.
8. Negative pregnancy test at study entry for females of childbearing potential.
9. Females must have a negative urine pregnancy test result at screening, prior to the start of the run-in period, at initiation of active dosing and every 4 weeks following till the end of the study. A negative urine and serum pregnancy test must be obtained prior to active dosing. Males and females of childbearing potential must use two methods of contraception, one of which must be a highly effective method from the time of screening to the last dosing study visit (22 weeks).

Highly effective methods include:

- o combined (estrogen and progestogen containing) hormonal contraception (oral, intravaginal or transdermal) associated with inhibition of ovulation
- o progestogen-only hormonal contraception (oral, injectable or implantable) associated with inhibition of ovulation
- o intrauterine device (IUD)
- o intrauterine hormone-releasing system (IUS)
- o bilateral tubal occlusion

Acceptable methods include:

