4.2 Exclusion Criteria

Subjects who meet any of the following criteria must be excluded from the study:

1. Patients with active (acute or chronic) liver disease other than NASH (e.g. viral hepatitis, genetic hemochromatosis, Wilson disease, alpha-1 antitrypsin deficiency, alcohol liver disease, drug induced liver disease) at the time of enrolment.
2. ALT or AST > 5 times ULN.
3. Abnormal synthetic liver function (serum albumin ≤ 3.5 gm%, INR > 1.3).
4. Known alcohol and/or any other drug abuse or dependence in the last five years.
5. Weight > 120 Kg
6. Known history or presence of clinically significant, cardiovascular, gastrointestinal, metabolic (other than diabetes mellitus), neurologic, pulmonary, endocrine, psychiatric, neoplastic disorder or nephrotic syndrome.
7. History or presence of any disease or condition known to interfere with the absorption, distribution, metabolism or excretion of drugs including bile salt metabolites (e.g. inflammatory bowel disease (IBD), previous intestinal (ileal or colonic) operation, chronic pancreatitis, celiac disease or previous vagotomy).
8. Weight loss of more than 5% within 6 months prior to enrolment.
9. History of bariatric surgery.
10. Uncontrolled blood pressure $BP \geq 150/ \geq 95$.
11. Non type 2 DM (type 1, endocrinopathy, genetic syndromes etc).
12. Patients with HIV.
13. Daily alcohol intake > 20 g/day (2 units/day) for women and > 30 g/day (3 units/day) for men.
14. Treatment with anti-diabetic medications other than at least one and no more than-three of the following medications: metformin, sulfonylurea, DPP-4 inhibitors, oral GLP-1 receptor agonists (semaglutide), SGLT-2 inhibitors, or TZDs
15. Fibrates and statins, not provided on a stable dose in the last 6 months.
16. Patients who are treated with valproic acid, Tamoxifen, methotrexate, amiodarone.
17. Chronic treatment with antibiotics (e.g. Rifaximin).
18. Homeopathic and/or Alternative treatments. Any treatment must be stopped before the screening period.
19. Uncontrolled hypothyroidism defined as Thyroid Stimulating Hormone $> 2X$ the upper limit of normal (ULN). Thyroid dysfunction controlled for at least 6 months prior to screening is permitted.
20. Patients with renal dysfunction: eGFR < 40 ml/min.
21. Unexplained serum creatinine phosphokinase (CPK) $> 3X$ the upper limit of normal (ULN). Patients with a reason for CPK elevation may have the measurement repeated prior to enrolment; a CPK retest $> 3X$ ULN leads to exclusion.

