22. Subjects meeting criteria for contraindication for MRI – including the following:
 - History of severe claustrophobia impacting ability to perform MRI during the study, even despite mild sedation/treatment with anxiolytic.
 - Subjects with metal implants, devices, paramagnetic objects contained within the body and excessive or metal containing tattoos.
 - Subjects unable to lie still within the environment of the MRI scanner or maintain a breath hold for the required period to acquire images, even despite mild sedation/treatment with anxiolytic.
23. Subject participated in a clinical research study involving a new chemical entity within 4 weeks of study entry.
24. Known allergy to soy

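### Section 7.6.1 says that breastfeeding women are excluded, but no entry criterion in Sections 4.1, 4.2 or the synopsis lists this, so the passages need to be reconciled

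*Combined protocol and SAP*

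**What the plan says.** Section 7.6.1, in the adverse-event chapter, lists potential risks of ORMD-0801. On lactation it says: "It is also not known whether this product is excreted in human milk". The next sentence reads: "Pregnant or breastfeeding women are excluded from this study".

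Eligibility is set in Section 4. Section 4.1 opens with "Each subject must meet all of the following criteria to be eligible for the study" and numbers 11 inclusion criteria. Section 4.2 opens with "Subjects who meet any of the following criteria must be excluded from the study" and numbers 24 exclusion criteria, the last being "Known allergy to soy". The synopsis repeats both lists with the same numbering.

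The criteria that bear on reproduction are inclusion criteria 8 and 9. Criterion 8 is "Negative pregnancy test at study entry for females of childbearing potential". Criterion 9 adds repeated pregnancy testing and two methods of contraception, and defines non-childbearing potential. Criterion 1 admits women of reproductive age: "Male or female aged 18-70 years".

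Section 3.2.1 defines a screen failure as a subject who has signed consent but "does not meet all the entry criteria outlined in Section 4 of this protocol".

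**The concern.** The safety chapter describes a protection for breastfeeding women that the lists used to decide entry do not contain. Staff normally check eligibility against the numbered criteria, not against a sentence under potential adverse events. If the sentence is overlooked, a woman whom the protocol says is excluded could be dosed, with an exposure to the infant that the protocol itself calls unknown.

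There is a smaller data question as well. If such a woman were enrolled, Section 4 and Section 7.6.1 would point different ways on whether she had been properly entered. Section 8.1.1 limits the Per Protocol population to subjects without major protocol deviations, so her place in it would be open to argument.

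**Working it through.** No arithmetic is involved beyond counting. The check is to see whether any entry rule or screening step implements the statement in Section 7.6.1.

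**Step 1: count the criteria that mention breastfeeding, lactation or nursing.**

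| Place | Criteria | Mention breastfeeding |
|---|---|---|
| Section 4.1, inclusion | 11 | 0 |
| Section 4.2, exclusion | 24 | 0 |
| Synopsis, inclusion | 11 | 0 |
| Synopsis, exclusion | 24 | 0 |

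Both lists run without gaps in both places, so the absence does not come from missing text. Section 7.6.1 is the only place in the document that mentions breastfeeding.

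**Step 2: ask whether another criterion covers it indirectly.**
- Inclusion criteria 8 and 9 deal with pregnancy and its prevention. A breastfeeding woman can have a negative test and use contraception, so neither identifies her.
- Exclusion criterion 6 concerns clinically significant disorders, which breastfeeding is not.
- Exclusion criterion 7 concerns diseases or conditions known to interfere with how drugs are handled. Section 7.6.1 says that excretion in milk is not known, so this criterion does not plainly apply.

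**Step 3: ask whether a screening procedure would reveal it.** The overall design (Section 3.1), the Visit 1 list (Section 3.2) and the schedule of events (Section 3.8) contain no breastfeeding question.

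**Step 4: compare the two halves of the sentence in Section 7.6.1.**

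| Element | Pregnancy | Breastfeeding |
|---|---|---|
| Entry criterion | Inclusion 8 and 9 | None |
| Check during the study | Section 6.5.7 | None |
| Reason to end participation | Section 4.3, item 3 | None |
| Reporting and follow-up | Sections 4.3 and 7.5.2 | None |

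**Step 5: identify what decides enrolment.** Section 4.1 ties eligibility to its own list, and Section 3.2.1 ties screen failure to Section 4. Section 9.3 asks source data to show that the inclusion and exclusion criteria were met. None of these refers to Section 7.6.1. A woman who meets the diabetes, imaging and other requirements is not stopped by any listed criterion because she is breastfeeding.

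**The case against.** The strongest reply is that Section 7.6.1 is itself protocol text. Section 10 requires the investigator to follow the procedures described in the protocol, and Section 11.2.3 denies authority to depart from it without prior approval, save for immediate hazards. An investigator who enrolled a breastfeeding woman would be acting against an express sentence and could be cited for a deviation. This stands. A reader might infer that the exclusion has no force; the documents do not support that. What is missing is a step at entry that applies it.

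It can also be said that Section 4 is silent rather than permissive. No criterion admits breastfeeding women, so a reader who concludes that the protocol makes them eligible goes too far. The lists are incomplete relative to Section 7.6.1; they do not state the opposite rule. Nor do the criteria rely on pregnancy tests alone, since criterion 9 also requires contraception, though this does not identify breastfeeding either.

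The eligibility CRF and the consent form are not available here, and either may already ask the question. That limits the point to the protocol text. It does not remove the mismatch within that text.

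Finally, the stakes are modest. The primary objective concerns safety in the enrolled patients, whereas the human-milk question concerns an infant, so the link between them is loose.

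**Conclusion.** The point holds as an internal inconsistency. The intention is stated once, in Section 7.6.1, and is absent from all 35 entry criteria (11 + 24) in Section 4 and from the same 35 in the synopsis. Because Section 3.2.1 defines screen failure by Section 4 alone, a site working from the entry lists could enrol a woman whom Section 7.6.1 says is excluded, and the protocol would not settle whether that was a deviation.

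The practical size is probably small. Enrolment is up to 40 patients aged 18 to 70, and the documents give no figure for how many might be breastfeeding. Sample size, endpoints and planned summaries are unaffected; the only analysis question is how such a subject would be classified for the Per Protocol population.

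The conclusion rests on the protocol text and assumes that sites screen from the numbered criteria. A CRF or consent form that already covers the matter would lower the practical risk, but the protocol would still need correcting.

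**What to change.** Make Section 7.6.1, Sections 4.1/4.2 and the synopsis state the same rule. Which rule is intended is for the sponsor to confirm.

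- If the Section 7.6.1 statement stands, carry it into Section 4.2 and the synopsis as a numbered criterion, and confirm that the eligibility CRF reflects it. A departure would then be a screen failure or an eligibility deviation without argument.
- If it does not stand, correct Section 7.6.1.

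The cost is about one line in each place, plus a check of the CRF, and can go into the next amendment. No visit, laboratory test or analysis needs to be added.

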7.7 Adverse Event Severity Assessment

The Principal Investigator will provide an assessment of the severity of each adverse reaction by recording a severity rating on the appropriate AE reporting page of the subject's CRF. Severity will be assessed according to the following scale:

Mild – events are usually transient and easily tolerated, requiring no special treatment and causing no disruption of the subject's normal daily activities.

Moderate – events introduce a low level of inconvenience or concern to the subject and may interfere with daily activities but are usually improved by simple therapeutic measures. Moderate experiences may cause some interference with functioning.

Severe – events interrupt the subject's normal daily activities and generally require systemic drug therapy or other treatment. They are usually incapacitating.

7.8 Expectedness of Adverse Event

An unexpected AE is defined in 21 CFR 312.32(a) as follows:

An AE is considered “unexpected” if it is not listed in the IB or is not listed at the specificity or severity that has been observed; or, if an IB is not required or available, is not consistent

with the risk information described in the general investigational plan or elsewhere in the current application, as amended.

7.9 Assessment of Adverse Event Outcome

Outcome of AEs will be defined according to ICH Topic E2B, ICH Guideline.

- **Recovered/Resolved:** The subject has recovered fully from the AE without any remaining effects or impairment.
- **Recovered/Resolved with Sequelae:** The subject has recovered, but with an after effect possibly due to disease or treatment.
- **Not Recovered/Not Resolved:** The condition is still present.
- **Fatal:** Fatal should only be used when death is possibly related to the AE.
- **Unknown:** The primary outcome is not known at the time of the final assessment. If an outcome for an AE is not available at the time of the initial report, follow-up will proceed until an outcome is known or followed up to the Final Study Visit. Any subject with a possible IMP-related AE at the Final Study Visit will be followed until resolution or stabilization of the event. Further, any SAE, whether or not related to IMP (active or Placebo), that occurs within 30 days following the last dose of IMP will be followed until resolution or stabilization of the event.

7.10 Clinical Findings

Any significant clinical findings at Visit 9 will be followed until the condition returns to pre-study status, stabilizes, or can be explained as not being IMP related. If the clinical finding is reported as an AE (per the criteria outlined in Section 7.2), the follow-up procedures for AEs defined above will apply.

8 STATISTICAL METHODS

This section describes the statistical methods to be used for the analysis and reporting of data collected under Protocol No. ORA-D-N01B. Additional details will be provided in the statistical analysis plan.

8.1 Sample Size

Up to 40 patients with NASH and Type 2 DM will be enrolled in this multi-center exploratory study. Approximately 20 patients will be enrolled at 2 sites in Israel, approximately 10 subjects will be enrolled at 3 or 4 sites in Belgium and 10 patients at 2 sites in the USA.

The treatment regimen will consist of a soft gelatin capsule containing 8 mg insulin, and 75 mg SBTI. Patients will take 2 capsules daily in the morning 30 to 45 minutes prior to breakfast.

The size of the study population was determined by reviewing the literature for pilot studies and was found to be sufficient to show trends of reducing liver fat content by MRI PDFF (MRI-Proton Density Fat Fraction) images and Fibroscan including CAP. This study is not powered for statistical significance.

8.1.1 Populations

Safety Population: All subjects who receive at least one dose of IMP will be included in the safety population.

Intention to Treat: All subjects who were received treatment were included in the Intention to Treat population.

Per Protocol: All subjects who completed all study visits without any major protocol deviations and took between 80% and 120% of Investigational Product were included in the Per Protocol population.

8.2 Safety Evaluation

8.2.1 Adverse Events

AEs will be coded using the most current version of MedDRA. The severity of AEs will be graded according to NCI CTCAE version 4.03. AEs will be regarded as “pretreatment” if they occur during the Placebo run-in period. TEAEs are defined as any AE that starts or increases in severity after the first dose of IMP at Visit 3.

The incidence of TEAEs will be tabulated by MedDRA preferred term, system organ class, treatment group, severity, and assigned relationship to IMP. The incidence for each TEAE will be provided as the total number of subjects that experienced the TEAE, as well as the percentage of the population that this represents. If a TEAE is reported more than once for a given subject, the greatest severity and the worst-case attribution will be presented in the summary tables.

TEAEs will be listed for individual subjects, along with information regarding onset and end dates, onset time where available, severity, seriousness, relationship to IMP, action taken, and outcome. A similar listing will be prepared for the pretreatment AEs.

Pretreatment AEs and TEAEs that lead to withdrawal from the study will be separately listed and summarized. Similarly, separate tabulations and listings will be prepared for pretreatment and treatment-emergent SAEs.

Descriptive statistics will be generated as appropriate (i.e., frequency for categorical data). Inferential statistical analysis comparing the AE data between Active treatment and Placebo is not planned.

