3.7 Self-Monitoring Fasting Blood Glucose and Patient Diaries

All patients will self-monitor fasting morning blood glucose levels three (3) times weekly during the run-in and treatment period. Monitoring must be performed at the same time each designated day (\pm 10 minutes) prior any caloric intake. Patients will be required to record the values in a patient diary and bring the diary to each clinic visit; Information recorded for the fasting blood glucose will be reviewed by the clinical research coordinator for completeness and transcribed onto CRF's. During the study, both fasting finger stick glucose and laboratory fasting plasma glucose will be obtained. Adverse events including hypoglycemia will be monitored from the self-monitoring blood glucose diary and recorded in the CRF.

If a fasting blood glucose measures greater than or equal to 270 mg/dL (15 mmol/L) during daily self-monitoring or during any in-clinic visit, the patient will be required to contact the clinic to report the value. The patient may be required to return for an unscheduled visit to the clinic for a repeat measurement of fasting blood glucose within one week after the original measurement. If the patient is invited for an unscheduled visit, blood will be drawn and sent to lab for plasma glucose determination. If the repeat measurement is also greater than or equal to 270 mg/dL, the patient will be discontinued from treatment with study drug and offered rescue medication. The patient will continue to be seen for all remaining study visits, if possible.

If a fasting blood glucose value is <70 mg/dL, the patient should drink 1 cup of orange juice or swallow 3-4 glucose tablets. The patient must check his blood sugar after 10 min and if the blood glucose level does not raise, the patients needs to drink another cup of orange juice or swallow 3-4 glucose tablets. Blood sugar must be checked again after 10 minutes. The patient must call to report this event to the study site and record all blood glucose levels in the diary.

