If three or more fingerstick glucose values of <50 mg/dL (2.78 mmol/L) are observed within 12 hours subsequent to administration of study drug without a reasonable explanation (such as increased physical activity and/or skipped meal), the patient will be discontinued from treatment with study drug and rescued with glucose administration (20g of glucose tablets) which will be available at all times at the study site. This information will be recorded in the patient's diary and

the patient will be instructed to contact the study site if this occurs. The patient will continue to be seen for all remaining study visits.

Sites will instruct patients to immediately perform a finger stick glucose measurement if any symptoms occur that may be related to hypoglycemia (e.g., weakness, dizziness, shakiness, increased sweating, palpitations, or confusion), and to avoid delay in treating these symptoms. The measurements will be recorded in the patient diary. Patients will always carry glucose tablets with them and ingest 3-4 tablets if hypoglycemia occurs.

Hypoglycemia and associated symptoms (e.g., weakness, dizziness, shakiness, increased sweating, palpitations, or confusion), have been associated with insulin administration, including ORMD-0801.

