6.3 Study endpoints

The primary endpoint of this trial will evaluate safety of ORMD-0801 in patients with nonalcoholic steatohepatitis (NASH) and type 2 DM.

Secondary endpoints will evaluate the effectiveness of ORMD-0801 in reducing liver fat content in patients with NASH and type 2 DM by measuring the final and baseline differences in the MRI as liver function tests.

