7.3 Adverse Events of Special Interest

7.3.1 Adverse Events of Hypoglycemia

The CTCAE (version 5.0) criteria for mild, moderate, and severe hypoglycemia based on blood glucose will be used, as shown below:

Mild: < 70 – 55 mg/dL (< 3.8 - 3.0 mmol/L)

Moderate: < 55 – 40 mg/dL (< 3.0 - 2.2 mmol/L)

Severe: < 40 – 30 mg/dL (< 2.2 - 1.7 mmol/L)

Life Threatening: < 30 mg/dL (< 1.7 mmol/L)

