7.5 Recording Adverse Events

All adverse events experienced during the trial, regardless of relationship to study medication, must be recorded on the Adverse Event CRF from the time of patient consent until completion of patients End of Study visit (Visit 9). All serious adverse events will be collected through Visit 9. The Investigator must continue to follow all non-serious events possibly related to the study medication and all serious adverse events until they resolve or until the Investigator assesses them in writing as chronic or stable.

Regardless of relationship to study medication, the event must be recorded on the Adverse Event CRF. Adverse event documentation should include the following information:

- Standard medical terminology for the AE
- Description of adverse event
- Date and time of onset
- Date and time of resolution of the adverse event
- Whether or not the event is ongoing
- Severity of the event
- Relationship between the adverse event and the investigational product
- Description of any actions taken (e.g., medications, treatments)
- Outcome of the AE
- Whether or not the effect was serious and/or unanticipated

Whenever possible, a diagnosis should be given when signs and symptoms are due to common etiology (e.g., cough, runny nose, sneezing, sore throat, and head congestion should be reported as "upper respiratory infection"). For the purposes of this study, hypoglycemic events will be considered adverse events and should be recorded in source and CRF records.

When a diagnosis is not available, each adverse event should be reported separately. For example, "nausea and vomiting" should be split into two separate events.

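### Hypoglycaemia is summarised only as patients with at least one event; Section 8 specifies no episode count or exposure-based rate

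*Combined protocol and SAP*

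**What the plan says.** Section 6.3 sets the primary endpoint: "The primary endpoint of this trial will evaluate safety of ORMD-0801". It names no variable or summary measure. Section 7.3 lists one adverse event of special interest, hypoglycaemia, and Section 7.3.1 bands it by glucose value: "The CTCAE (version 5.0) criteria for mild, moderate, and severe hypoglycemia based on blood glucose will be used".

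Collection is at episode level. Section 7.5 states "For the purposes of this study, hypoglycemic events will be considered adverse events", and Section 3.7 adds "Adverse events including hypoglycemia will be monitored from the self-monitoring blood glucose diary and recorded in the CRF". Fasting self-monitoring takes place three times a week through run-in and treatment, and the values are transcribed to the CRF.

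Section 8.2.1 governs the summary. "The incidence for each TEAE will be provided as the total number of subjects that experienced the TEAE", with the matching percentage. Repeats are handled thus: "If a TEAE is reported more than once for a given subject, the greatest severity and the worst-case attribution will be presented". The same section plans by-subject listings of treatment-emergent events with dates, severity, relationship, action and outcome, and a similar listing for run-in events. Section 8 contains no rule specific to hypoglycaemia.

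**The concern.** Hypoglycaemia can recur in the same patient under daily dosing, and Sections 3.7 and 7.6.1 name it as a known effect of insulin, including ORMD-0801. The protocol itself treats repetition as informative: Section 3.7 attaches an action to a cluster of low values, beginning "If three or more fingerstick glucose values of <50 mg/dL (2.78 mmol/L) are observed within 12 hours". Yet in the planned table a patient with one mild reading and a patient with many mild episodes each contribute one count at the same severity.

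What is at stake is whether the report of a safety-primary study can say, in a summarised result, how many hypoglycaemic episodes occurred, how they were spread over patients, and how often they occurred per unit of time on drug. The only within-study reference is the placebo run-in, which lasts one sixth as long as treatment. Raw percentages of patients affected in the two periods are therefore not on a common scale.

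**Working it through.** **Inputs from the documents.** Up to 40 patients, single arm and open label (Sections 3.1 and 8.1); 2-week placebo run-in (3.3); 12 weeks of treatment (3.4); three scheduled fasting readings a week (3.7). The plan gives no hypoglycaemia rate, dispersion, power or effect size, so it has no figure on this point to reproduce. The site split in 8.1 does add up: 20 + 10 + 10 = 40.

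**Assumptions.** All 40 patients complete both periods. The share affected, the episode rates and the dispersion are illustrative and are shown as ranges.

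**Step 1: exposure.** Treatment: 40 × 12 / 52 = 9.23 patient-years. Run-in: 40 × 2 / 52 = 1.54 patient-years. Scheduled readings per patient: 3 × 12 = 36 on treatment and 3 × 2 = 6 in run-in.

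**Step 2: recurrence within affected patients (no model needed).** Suppose 10 of 40 (25%) are affected. With 1, 2, 5 or 10 episodes each, the totals are 10, 20, 50 or 100. Divided by 9.23 patient-years, the rates are 1.08, 2.17, 5.42 or 10.83 per patient-year. The planned table shows 10 (25%) in all four cases.

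**Step 3: how far the percentage follows a doubled rate.** Suppose 30% (12 of 40) have at least one episode, so the probability of none is 0.70. Let μ be the mean number of episodes per patient over 12 weeks.
- Poisson: μ = −ln 0.70 = 0.357. At 2μ, the share affected is 1 − 0.70² = 51.0%.
- Negative binomial with size k (smaller k means episodes concentrated in fewer patients): μ = k(0.70^(−1/k) − 1). At 2μ, the share affected is 1 − (1 + 2μ/k)^(−k).

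| Model | μ | Episodes in 40 patients | Affected at μ | Affected at 2μ |
|---|---|---|---|---|
| Poisson | 0.357 | 14.3 | 30% | 51.0% |
| k = 0.5 | 0.52 | 20.8 | 30% | 43.0% |
| k = 0.2 | 0.99 | 39.6 | 30% | 38.0% |
| k = 0.1 | 3.44 | 137.6 | 30% | 34.6% |

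The same 30% is compatible with about 14 to 138 episodes. When episodes double, the percentage rises by less than a factor of two in every row, and by less the more they cluster.

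**Step 4: run-in against treatment.** Take a constant 0.05 episodes per week, Poisson, with no drug effect. Run-in: 1 − exp(−2 × 0.05) = 9.5%. Treatment: 1 − exp(−12 × 0.05) = 45.1%. The gap comes from duration alone; the rate per week is the same in both periods.

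**The case against.** The strongest reply is that little is hidden. With at most 40 patients in one arm, a reader can count repeats from the dated by-subject listings. A higher rate usually brings in more affected patients, so the table does move. Section 8.2.7 promises descriptive statistics for all data, and the opening of Section 8 defers further detail to a statistical analysis plan, of which no separate text is in the documents. The study is exploratory and not powered, and Section 8.2.1 rules out inferential comparison of adverse events between active drug and placebo.

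Much of this stands, and it limits the point. Three stronger readings are tempting, and the documents do not support them:
- A reader might infer that repeat episodes appear nowhere. They appear in the listings; what is missing is a summary of them.
- A reader might infer that the percentage barely responds to a higher rate. That depends on strong clustering, which the documents neither state nor exclude. Under Poisson, doubling the rate moves 30% to 51%.
- A reader might infer that the treatment-emergent definition drops more frequent events because it mentions only events that start or worsen. Each new episode after the first Visit 3 dose does start after dosing, so it qualifies and is listed. The loss comes from the one-entry-per-subject rule in the tables.

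The rest of the reply does not remove the gap. General wording about descriptive statistics commits to no episode count, no distribution per patient and no rate, whereas 8.2.1 states a definite counting rule that works the other way. A descriptive, unpowered design argues against tests, not against reporting how many episodes occurred.

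**Conclusion.** The point holds as a gap in the summary measure. For the only adverse event of special interest, Section 8.2.1 fixes a count of subjects with repeats collapsed, and nothing else in Section 8 specifies an episode count or an exposure-based rate. Recurrence in patients already affected is lost entirely from the tables, and a higher rate shows only in part, to a degree that depends on clustering. Percentages from run-in and treatment are not comparable without exposure.

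The sizes rest on assumed rates, full follow-up and an assumed range of k; the direction does not depend on the particular values. Even with rates, the run-in comparison remains descriptive, because the run-in always comes first and there is no concurrent control. It cannot be said that the final analysis will omit episode counts, since a later analysis plan could add them. This is a worthwhile, inexpensive improvement to a safety-primary study, not an error that invalidates the planned tables.

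**What to change.** In Section 8.2.1 (or the analysis plan), keep the subject incidence and add for hypoglycaemia, by the glucose bands of 7.3.1:

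1. The number of episodes, and the number of patients with 1, 2 and 3 or more.
2. Episodes per patient-time with the exposure shown, separately for run-in, on ORMD-0801 and after stopping drug. The last needs its own line because Section 3.7 keeps patients in follow-up after study drug is stopped. Any interval should allow for clustering within patients, for example by a robust variance; with about 40 patients a dispersion parameter would be poorly estimated, so simple counts come first.
3. Scheduled fasting diary readings below each limit, as a fraction of scheduled readings taken. Leave out rechecks and symptom-triggered readings, which would count one episode several times.

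State a data rule for when consecutive low readings form one episode; Section 3.7 calls for rechecks after 10 minutes, so the count is undefined without it. Reconcile the CTCAE version named in 7.3.1 (5.0) with that in 8.2.1 (4.03), so that the severity bands in the table are unambiguous.

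Cost: one more table, the episode rule, and some reconciliation of adverse event records with diary readings. No new visit, procedure or patient is needed. The reported burden of hypoglycaemia may look less favourable.
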